## 9.5. Safety Assessments

Safety and tolerability will be assessed on an ongoing basis by monitoring adverse events (AEs) (including any serious AEs [SAEs], AEs leading to withdrawal, injection-site reactions [ISRs], and any other dose-limiting toxicities [DLTs]), physical examinations/vital signs, changes in clinical laboratory values, and ECG results.

A DMC composed of qualified medical/clinical representatives will review the clinical data each time 3 new subjects complete treatment. The DMC will provide recommendations to the Sponsor regarding the acceptability of continued enrollment in the study and whether any modifications are warranted.

Safety will be assessed with the following parameters:

- Reported AEs (see [Section 9.6](#)) and concomitant medications (see [Section 7.2](#))
- Vital signs (including body weight, blood pressure, heart rate, temperature, and respiratory rate)
- Physical examination
- ECG
- Clinical laboratory tests (chemistry, hematology, and urinalysis)
- Pregnancy test

### 9.5.1. Vital Signs

Vital signs, including blood pressure (systolic and diastolic, in mmHg), body temperature (in °C), heart rate (in beats per minute), and respiratory rate (in breaths per minute) will be recorded with the subject in a sitting position after having rested for 5 minutes.

### 9.5.2. Physical Examination

A full physical exam will include, but not be limited to, an examination of general appearance, skin, HEENT (head, eyes, ears, nose, throat), lungs, heart, abdomen, back, lymph nodes, extremities, and basic nervous system evaluation.

Information about the physical examination must be present in the source documentation at the study site. Significant findings that are present prior to the start of study drug must be included in the medical history / current medical conditions page of the eCRF.

Significant findings made after the start of study drug that meet the definition of an AE must be recorded on the AE page of the eCRF.

### 9.5.3. Electrocardiogram

Standard 12-lead ECGs will be performed. The Subject ID and the subject's initials or date of birth (as permitted by applicable practice), the date and actual time of the tracing, and the study code must appear on each page of the tracing. Tracings will be dated, signed, and interpreted by a qualified physician.

The overall interpretation will be collected with a Yes / No statement about whether any clinically significant abnormalities are present that need to be specified further in the source document and eCRF.

Original ECG tracings, appropriately signed, will be archived at study sites.

#### **9.5.4. Clinical Laboratory Tests**

Blood samples will be drawn for chemistry and hematology. Urine samples will be collected for urinalysis and urine drug screen. Details on sample collection and processing will be described in the laboratory manual.

#### **9.5.5. Pregnancy Tests**

For each female of childbearing potential, a serum pregnancy test will be performed at Visit 1 (Screening) and a urine pregnancy test will be performed at visits specified in the Schedule of Events and at the discretion of the Investigator (e.g., for a subject with irregular menses).

The result of the serum pregnancy test at Screening and the urine pregnancy test at Visit 2 (Baseline) must be received before a subject may be enrolled during Visit 2.

### **9.6. Adverse Events and Serious Adverse Events**

#### **9.6.1. Definition of Adverse Event**

An AE is any untoward medical occurrence associated with the use of a drug in humans, whether or not considered drug related. An AE (also referred to as an adverse experience) can be any unfavorable and unintended sign (e.g., an abnormal laboratory finding), symptom, or disease temporally associated with the use of a drug and does not imply any judgment about causality.

An AE can arise with any use of the drug (e.g., off-label use, use in combination with another drug) and with any route of administration, formulation, or dose, including an overdose. An overdose with symptoms should be recorded as an AE.

A worsening of previous illness or condition from baseline while participating in the study is also considered an AE.

#### **9.6.2. Definition of Serious Adverse Event**

An SAE is any event that meets any of the following criteria:

- Results in death
- Is life-threatening
- Requires inpatient hospitalization or prolongation of existing hospitalization
- Results in persistent or significant disability/incapacity
- Is a congenital anomaly/birth defect
- Is an important medical event. An important medical event that may not result in death, be life-threatening, or require hospitalization may be considered SAEs when, based upon appropriate medical judgment, the event may jeopardize the subject or require medical or surgical intervention to prevent one of the other outcomes listed in the definition above.

Examples of such medical events include allergic bronchospasm requiring intensive treatment in an emergency room or at home, blood dyscrasias or convulsions that do not result in inpatient hospitalization, or the development of drug dependency or drug abuse.

If, during follow-up, any non-serious AE worsens and eventually meets the criteria for an SAE, that AE should be recorded as a new SAE.

### **9.6.3. Classification of an Adverse Event**

#### **9.6.3.1. Severity**

The Investigator will provide an assessment of the severity of each AE by recording a severity rating on the AE page of the subject's eCRF. Severity, which is a description of the intensity of manifestation of the AE, is distinct from seriousness. Severity will be assessed according to the following scale:

- **Mild:** A type of AE that is usually transient and may require only minimal treatment or therapeutic intervention. The event does not generally interfere with usual activities of daily living.
- **Moderate:** A type of AE that is usually alleviated with additional specific therapeutic intervention. The event interferes with usual activities of daily living, causing discomfort, but poses no significant or permanent risk of harm to the subject.
- **Severe:** A type of AE that interrupts usual activities of daily living, or significantly affects clinical status, or may require intensive therapeutic intervention.

#### **9.6.3.2. Relationship to Study Drug**

The Investigator must assess the relationship of each AE to the study drug according to the categories defined below and record it on the AE page of the subject's eCRF.

- **Definitely Related:** There is clear evidence to suggest a causal relationship, and other possible contributing factors can be ruled out. The clinical event, including an abnormal laboratory test result, occurs in a plausible time relationship to study drug administration and cannot be explained by concurrent disease or other drugs or chemicals. The response to withdrawal of the study drug (dechallenge) should be clinically plausible. The event must be pharmacologically or phenomenologically definitive, with use of a satisfactory rechallenge procedure if necessary.
- **Probably Related:** There is evidence to suggest a causal relationship, and the influence of other factors is unlikely. The clinical event, including an abnormal laboratory test result, occurs within a reasonable time after administration of the study drug, is unlikely to be attributed to concurrent disease or other drugs or chemicals, and follows a clinically reasonable response on withdrawal (dechallenge). Rechallenge information is not required to fulfill this definition.
- **Possibly Related:** There is some evidence to suggest a causal relationship (e.g., the event occurred within a reasonable time after administration of the study drug). However, other factors may have contributed to the event (e.g., the participant's clinical condition, other concomitant events). Although an AE may rate only as "possibly related" soon after

discovery, it can be flagged as requiring more information and later be upgraded to “probably related” or “definitely related”, as appropriate.

- **Unlikely to be related:** A clinical event, including an abnormal laboratory test result, whose temporal relationship to study drug administration makes a causal relationship improbable (e.g., the event did not occur within a reasonable time after administration of the study intervention) and in which other drugs or chemicals or underlying disease provides plausible explanations (e.g., the participant’s clinical condition, other concomitant treatments).
- **Not Related:** The AE is completely independent of study drug administration, and/or evidence exists that the event is definitely related to another etiology. There must be an alternative, definitive etiology documented by the clinician.

This assessment will help the Sponsor to determine whether an AE might be a suspected adverse reaction. A suspected adverse reaction is any AE for which there is a reasonable possibility that the drug caused the AE. ‘Reasonable possibility’ means there is evidence to suggest a causal relationship between the drug and the AE. A ‘suspected adverse reaction’ implies a lesser degree of certainty about causality than ‘adverse reaction’.

The Investigator may change the causality assessment at any time based on new accumulated information. An AE with causal relationship not initially determined will require follow-up to assign causality.

#### **9.6.3.3. Expectedness**

An unexpected AE or unexpected, suspected adverse reaction refers to an event or reaction that is not listed in the Reference Safety Information section of the most recent version of the IB or is not listed at the specificity or severity that has been observed. The Sponsor will be responsible for determining whether an AE is expected or unexpected.

#### **9.6.4. Time Period and Frequency for Event Assessment and Follow-up**

AEs will be recorded from the time the ICF is signed until the subject completes the last study visit or withdraws from the study.

AEs will be assessed at each study visit, and subjects should be encouraged to report any AEs at their onset. Study staff will elicit information about AEs using nonspecific questions such as “Have you experienced any change in your health status since your last visit?” Subjects will also be monitored closely for the development of an AE.

Any AE or clinically significant abnormality of ECG, physical examination finding, or clinical laboratory measurement that occurs during the study should be followed until no further medical intervention is warranted (e.g., it resolves, becomes medically stable, or is assessed as chronic) or until the subject is lost to follow-up. AE follow-up must comply with International Council for Harmonisation (ICH) Good Clinical Practice (GCP) guidelines.

#### **9.6.5. Adverse Event Reporting**

Information about AEs will be recorded on the AE page of the subject’s eCRF. When known, the diagnosis (rather than individual symptoms) should be entered as the event term in the eCRF. For

example, an upper respiratory infection with symptoms of cough, rhinitis, and sneezing should be recorded as upper respiratory infection. When the diagnosis is unclear, key symptoms may be entered separately, and the Investigator should obtain appropriate tests to establish a diagnosis, if possible. After a diagnosis is determined, the eCRF event term should be updated.

For each AE, the onset date, seriousness, severity (Section 9.6.3.1), relationship to study drug (causality) (Section 9.6.3.2), action taken, outcome, and date of resolution (or continuing) will be recorded. The Investigator must make a causality assessment for each AE.

#### **9.6.6. Serious Adverse Event Reporting and Follow-up**

Any SAE, including death, due to any cause, that occurs from the time the ICF is signed until 4 weeks after a subject's last dose of study drug must be reported to the Sponsor or its designee within 24 hours of the study center staff learning of its occurrence.

The Sponsor is required to inform worldwide regulatory authorities of SAEs that meet specific criteria and to do so in an expedited fashion. Specifically, suspected, unexpected serious adverse reactions (SUSARs) are subject to expedited safety reporting requirements. The Sponsor will report applicable SAEs to the appropriate authorities within the timelines and format required by local regulations. Therefore, the Sponsor must be notified of any SAE that occurs after informed consent is obtained within 24 hours of the study center staff learning of its occurrence.

An SAE Form must be completed and reported via email at [[contact]](mailto:[contact]). All SAEs must be recorded on the AE page of the eCRF, marking the event as serious within the form. All relevant seriousness criteria should be recorded, and relationship to study drug should be assigned at the time of initial report, as this is required to determine regulatory reporting.

SAEs must also be reported to the Institutional Review Board (IRB) / Independent Ethics Committee (IEC) according to the requirements of the IRB/IEC.

The Investigator is expected to institute appropriate diagnostic and therapeutic measures necessary to treat and promote resolution of the SAE. Any medications or procedures used to treat the SAE must be recorded on the appropriate pages of the subject's eCRF. The Investigator must determine whether the seriousness of the event warrants discontinuation of study drug.

The Investigator is expected to proactively follow up on the SAE with the subject at subsequent visits/contacts. All SAEs will be followed until no further medical intervention is warranted (e.g., the event resolves, becomes medically stable, or is assessed as chronic) or until the subject is lost to follow-up. Follow-up information on the SAE will also be reported using the AE eCRF.

The Sponsor or designee may contact the study center to solicit additional information or follow up on the event. If requested, medical records (such as laboratory results, radiology reports, progress notes, hospital admission and emergency room notes, holding and observation notes, discharge summaries, autopsy reports, and death certificates) should be emailed to the safety inbox after redacting all information that personally identifies the subject or hospital staff (per the European Global Data Protection Regulation).

After 4 weeks after a subject's last dose of study drug, the Investigator is not obligated to actively seek AEs or SAEs. However, if the Investigator learns of any SAE, including a death, at any time after a subject has been discharged from the study, and he/she considers the event

reasonably related to the study drug or to study participation, the Investigator must notify the Sponsor or designee within 24 hours of learning of the event.

## **9.7.      Pregnancy**

Any pregnancy in a female subject or in the partner of a male subject that occurs from the time the subject signs an ICF until 90 days after the final application of study drug must be reported to AmMax or its designee within 24 hours of learning of its occurrence. A pregnant female subject will be immediately discontinued from study drug.

The subject or pregnant partner should provide consent and be followed throughout the course of the pregnancy. Pregnancy follow-up information, including the outcome of the pregnancy, should be reported to AmMax or its designee.

## **9.8.      Pharmacokinetic Assessments**

Serum and synovial fluid will be collected from all subjects to assess AMB-05X concentrations and anti-drug antibody formation at the visits indicated in the Schedule of Events.

## **9.9.      Blood and Synovial Fluid Sampling**

All blood samples will be taken by direct venipuncture. Details on sample collection and processing will be described in a separate laboratory manual. Blood sampling volumes will be limited by the most stringent regulations applicable to a particular site or region.

Synovial fluid (2 mL) will be collected from the affected joint prior to injection of study drug at Weeks 0, 2, 4, 6, 8, and 10. The expected total sampling volume over the course of the study is up to 12 mL.

## **10. STATISTICS**

### **10.1. General Considerations**

All study data will be summarized by treatment using descriptive statistics. Unless otherwise specified, descriptive statistics for numeric data (e.g., age, weight) will include the number of subjects with data to be summarized (n), mean, standard deviation (SD), median, minimum, and maximum. Categorical/qualitative data (e.g., sex, race) will be presented using absolute and relative frequency counts and percentages. All summaries, statistical analyses, and individual subject data listings described below will be completed using Version 9.3 or later of SAS software (SAS Institute, Inc., Cary, North Carolina).

A detailed final SAP will be provided separately. The SAP will be finalized prior to the first DMC meeting.

### **10.2. Sample Size Determination**

Based on prior Phase 1 experience and an anticipated treatment effect with AMB-05X in this population, the sample size of approximately 12 subjects is anticipated to provide sufficient data for PK/PD analysis and an estimate of safety, tolerability, and efficacy.

### **10.3. Efficacy Analyses**

Efficacy endpoints will be summarized using descriptive statistics and 95% confidence intervals. Exploratory hypotheses testing may be conducted using a significance level of 0.05 without adjustment for multiplicity.

### **10.4. Pharmacokinetic Analysis**

AMB-05X concentration data will be summarized by collection time. PK parameters will be deduced where possible by WinNonlin analysis.

### **10.5. Safety Analyses**

Safety analyses will include all subjects who received at least 1 dose of study drug.

The number of subjects exposed to each treatment group and the duration of exposure will be summarized.

All AEs reported will be listed, documenting severity, start and stop date and time, possible relationship to study drug, action taken, and outcome. TEAEs are defined as AEs recorded after first dose of study drug. Verbatim terms will be mapped to Preferred Terms (PTs) and related System Organ Classes (SOCs) using Medical Dictionary for Regulatory Activities (MedDRA). PTs and SOCs will be tabulated by treatment group. All reported AEs will be summarized by the number of subjects reporting AEs, SOC, PT, severity, and relationship to study drug. Multiple occurrences of an AE will be counted only once per subject per SOC and PT in summary tables.

The following TEAEs will be summarized by SOC, PT, and treatment group:

- Incidence of all TEAEs
- Incidence of all TEAEs by maximum severity (severe, moderate, and mild) specified by investigators

- Incidence of TEAEs related to the study drug as determined by the investigators
- Incidence of serious TEAEs
- Incidence of TEAEs leading to early discontinuation withdrawn from study

Safety labs (including hematology, chemistry, and urinalysis) will be tabulated using descriptive statistics. Abnormal/out-of-range findings and changes from pre-dose to post-dose will be listed by subject. Shift tables in all laboratory variables will be provided.

Vital signs and ECGs will be tabulated using descriptive statistics. Abnormal/out-of-range findings and changes from pre-dose to post-dose will be listed by subject. For ECG parameters, heart rate, RR, PR, QRS, and QT corrected with Fridericia's formula (QTcF) will be summarized by treatment group.

Concomitant medication usage will be summarized by treatment group. The World Health Organization Drug Dictionary will be used to classify concomitant medications by therapeutic class and generic name based on ATC (Anatomical Therapeutic Chemical) code level 3. A subject will only be counted once in each unique ATC class and generic name if the subject uses multiple drugs.

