Study Design	
This is a multicenter study with an adaptive design that will enroll approximately 12 subjects with TGCT of the knee for 12 weeks of multiple-dose, open-label treatment with AMB-05X.
 
The study schema is provided in Section 1.2, and the Schedule of Events is provided in Section 1.3. There will be a screening period of up to 4 weeks, a treatment period of 12 weeks, and a post-treatment follow-up period of 12 weeks. Clinic visits will occur at Screening (Visit 1, within 4 weeks prior to Baseline); Baseline/Week 0 (Visit 2, when subjects receive their first injection of AMB-05X); Week 2 (Visit 3); Week 4 (Visit 4); Week 6 (Visit 5); Week 8 (Visit 6); Week 10 (Visit 7, when subjects receive their last injection of AMB-05X); Week 12 (Visit 8, end of treatment period and assessment of primary and secondary endpoints); Week 14 (Visit 9, for post-treatment follow-up 2 weeks after completing the treatment period); and Week 24 (Visit 10, for final post-treatment follow-up 12 weeks after completing the treatment period).
 
The study will begin dosing AMB-05X at 150 mg administered via intra-articular injection to the affected knee joint. Subjects will receive an injection of AMB-05X once every 2 weeks for 12 weeks (for 6 treatments total).
 
Safety, pharmacokinetics (PK), pharmacodynamics (PD), and efficacy assessments will be reviewed by the Sponsor on a continuous, subject-by-subject basis to determine whether the assigned dose is appropriate. Depending on these results, the Sponsor may either decrease the dosage strength to 90 mg or increase the dosage strength to 210 mg in subsequent subjects who enroll. In general, subjects are expected to complete the study at the dose strength which they started the study, unless they experience a clinically significant AE that would warrant a dose reduction. As a general rule, clinically significant AEs include, but are not limited to, any AE considered to be at least possibly related to study drug and severe in intensity or meets the criteria for a SAE. Subjects who are unable to tolerate a dosage strength of 90 mg will be withdrawn from the study.
 
When at least 3 subjects have completed Week 6, a data monitoring committee (DMC) will review the available safety, tolerability, PK, PD, and efficacy data. Study enrollment and conduct may continue unchanged during DMC review. Based on the recommendations of the DMC, the Sponsor may then implement any one of the following adaptive changes without a protocol amendment:
 

• Continuation of enrollment under the existing design, without any changes to the study.

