### 2.3.3. Toxicology

In the in vivo toxicology studies in the cynomolgus monkey, animals received up to 300 mg/kg, IV, weekly for 4 or 14 weeks. In the 4-week and in both 14-week studies, all direct AMB-05X-related findings were attributed to the expected pharmacology of inhibition of macrophages. Additionally, changes related to the acute post-dosing formation of ADA/drug complex (also called circulating immune complexes [CICs]) occurred in some animals on the 14-week study.

Clinical observations attributed to AMB-05X pharmacology consisted of reversible periorbital swelling due to increased extracellular matrix as observed by light microscopy. Clinical pathology changes included reversible increases in serum ALT, AST, and glutamate dehydrogenase (GLDH) without a light microscopic correlate in the liver and without elevations in sorbitol dehydrogenase (SDH), a liver-specific marker of injury. The increased extracellular matrix and elevated activities of serum enzymes are considered to result from decreased clearance due to inhibition of macrophages (Radi, 2011). Additional AMB-05X-related changes included decreased bone turnover, characterized by elongation of bone growth plates and decreased number of osteoclasts, and decreases in serum markers of bone turnover, both of which were reversible. The presence of yeast organisms in the lung and protozoal organisms in the gastrointestinal tract in a few animals (contributing to death in 1 animal) may be incidental or a pharmacologic effect of AMB-05X. Increased neutrophil counts occurred in association with myeloid hyperplasia.

During the last 2 months of the dosing phase in the 14-week study, acute post-dosing sequelae (platelet effects and clinical signs including death) were observed in ADA-positive animals at 10 and 50 mg/kg. The role of ADA/drug complexes in the acute post-dosing findings was confirmed by demonstration of ADA/drug complexes serologically and immunohistochemically. No post-dosing CICs or related effects occurred at 300 mg/kg. Retrospective analyses correlating

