#### **3.1. Primary Endpoint**

The primary outcome measure is the frequency and severity of reported TEAEs.

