### **8.3. Study Drug Administration**

After confirmation of enrollment eligibility at Visit 2 (Baseline), subjects will be enrolled into the study and receive the first dose of study drug.

The study will begin dosing AMB-05X at 150 mg administered via intra-articular injection to the affected joint. Based on ongoing review of the available safety, PK, PD, and efficacy data, the Sponsor may decrease the dose to 90 mg or increase the dose to 210 mg in subsequent subjects. A separate Study Drug Administration Instructions will be provided with detailed study drug administration procedures.

A single vial will be removed from the kit [REDACTED]

[REDACTED] prior to administration. [REDACTED] [REDACTED], diluted with [REDACTED] mL normal saline (0.9% NaCl solution), and mixed gently prior to injection. AMB-05X must be administered within [REDACTED] hours from the beginning of the warming procedure. For a dose of 150 mg, a total of [REDACTED] mL of the diluted solution will be withdrawn from the vial in a sterile syringe and administered via an intra-articular injection to the affected knee joint. For a dose of 210 mg, [REDACTED] mL of the diluted solution will be withdrawn, and for a dose of 90 mg, [REDACTED] mL of the diluted solution will be withdrawn.

Eligible subjects will receive the intra-articular injection of AMB-05X to the affected knee joint once every 2 weeks for 12 weeks (for 6 treatments total). The Sponsor may change the dose based on its own ongoing review or periodic DMC review of available data (each time 3 new subjects complete study treatment).

Study drug will be administered at the study center by qualified study staff. Subjects will remain at the study center for a minimum of 90 minutes after dosing to monitor for any adverse reactions, including any injection-site reactions.

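### TEAE frequency over six knee injections is a primary measure, but the planned summary tables count subjects once per term and do not show recurrence or relate reactions to injections given

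*Combined protocol and SAP*

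**What the plan says.** Section 3.1 of the protocol states: "The primary outcome measure is the frequency and severity of reported TEAEs". No section says whether frequency means subjects, events or a rate. Section 8.3 plans six injections per subject, one every two weeks, into the affected knee.

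Section 10.5 sets the unit of the summaries: "All reported AEs will be summarized by the number of subjects reporting AEs, SOC, PT, severity, and relationship to study drug". It adds that "Multiple occurrences of an AE will be counted only once per subject per SOC and PT in summary tables". It then names five TEAE tables, all of incidence. One of them is "Incidence of all TEAEs by maximum severity (severe, moderate, and mild) specified by investigators".

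Exposure appears once, on its own: "The number of subjects exposed to each treatment group and the duration of exposure will be summarized". It is not a denominator for any AE table. Section 9.5 names injection-site reactions among the safety measures, and Section 8.3 requires observation for them after each dose, but Section 10.5 has no table for them.

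Section 10.5 also plans a listing of every AE with severity, start and stop date and time, relationship, action and outcome. Section 10.1 announces a separate SAP, to be final before the first DMC meeting. That SAP is not in the text reviewed.

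The time frame is not uniform. TEAEs begin at the first dose with no stated end (Section 10.5). Section 9.6.4 has AEs recorded up to the last visit or withdrawal. Section 9.6.6 says that from 4 weeks after the last dose the investigator need no longer look for them actively. The Synopsis lists "Week 12 (Visit 8, end of treatment period and assessment of primary and secondary endpoints", while Section 4.1 speaks at the same place of primary and secondary efficacy endpoints, although the protocol has no primary efficacy endpoint.

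**The concern.** For a drug injected repeatedly into the same joint, part of the tolerability question is whether a reaction happens once or returns with each injection. A once-per-subject count does not answer that, because one reaction and six reactions under the same term give the same entry.

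The count also depends on how many injections a subject has had. That varies if subjects stop early, and it varies by design when a dose is changed. Under Section 4.1 the DMC looks at a new dose once 3 subjects have completed Week 6 on it. Those subjects will have had up to 4 injections (Weeks 0, 2, 4 and 6), while subjects at the earlier dose may have had all 6. At the same risk per injection, the group with fewer injections would tend to show a lower incidence.

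**Working it through.** **Inputs from the protocol.** About 12 subjects (Section 10.2). Injections at Weeks 0, 2, 4, 6, 8 and 10, which is 6 per subject and reproduces the stated total; 12 × 6 = 72 injections if all are given. The sample size comes with no event rate or precision target, so there is no further figure to reproduce.

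**Inputs assumed.** The protocol gives no reaction rate for this drug given into a joint, so per-injection risks of 5% to 30% are used for illustration. All reactions are taken to code to the same PT.

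**Step 1: one reaction against six.** Subject incidence = affected subjects / 12. Per-injection rate = injections followed by a reaction / 72.

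| Affected subjects | Reactions each | Planned table | Events | Per injection |
|---|---|---|---|---|
| 3 | 1 | 3/12 = 25.0% | 3 | 3/72 = 4.2% |
| 3 | 6 | 3/12 = 25.0% | 18 | 18/72 = 25.0% |
| 12 | 1 | 12/12 = 100% | 12 | 12/72 = 16.7% |
| 12 | 6 | 12/12 = 100% | 72 | 72/72 = 100% |

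The planned entry is identical within each pair (for 3/12 the exact 95% interval is 5.5% to 57.2% both times), while the event count differs six-fold.

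**Step 2: unequal numbers of injections.** With independent injections, the chance that a subject is counted after m injections is 1 − (1 − p)^m.

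| p | m = 1 | m = 4 | m = 6 |
|---|---|---|---|
| 5% | 5.0% | 1 − 0.95^4 = 18.5% | 1 − 0.95^6 = 26.5% |
| 10% | 10.0% | 1 − 0.90^4 = 34.4% | 1 − 0.90^6 = 46.9% |
| 20% | 20.0% | 1 − 0.80^4 = 59.0% | 1 − 0.80^6 = 73.8% |
| 30% | 30.0% | 1 − 0.70^4 = 76.0% | 1 − 0.70^6 = 88.2% |

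At p = 10%, a group seen after 4 injections shows 34% and a group seen after 6 shows 47%, with no difference in risk per injection.

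**Step 3: the independence assumption.** If reactions cluster completely, so that the same 10% of subjects react every time, incidence is 10% after 4 injections and after 6. The comparability problem of Step 2 then disappears, but Step 1 is at its worst, because every affected subject reacts six times and is counted once. In between, both problems are present in part.

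**Step 4: time window.** The last dose is at Week 10, so 4 weeks later is Week 14. A single TEAE count to Week 24 joins Weeks 0 to 14 with 10 further weeks (24 − 14) in which Sections 9.6.4 and 9.6.6 differ on whether AEs are actively sought.

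**The case against.** Once-per-subject counting is a common convention, and the trial is small and descriptive. With about 12 subjects and at most about 72 injections, a reader of the dated listing can see who reacted six times and when. Dose decisions rest on continuous subject-by-subject review by the sponsor and on the DMC (Section 4.1), not on these tables. The endpoint includes severity, and the tables of maximum severity and of related, serious and discontinuation TEAEs address part of tolerability. The separate SAP may add event counts. All of this stands. It limits the consequence, but it does not put recurrence or injections given into any summary of the primary endpoint.

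Three stronger readings are tempting, and the documents do not support them.

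- A reader might infer that a badly tolerated regimen would pass as a tolerable one. The listing and the severity tables work against that.
- A reader might take the monkey data as a forecast of late reactions in the knee, since Section 2.3.3 reports effects "During the last 2 months of the dosing phase in the 14-week study, acute post-dosing sequelae". Those animals had weekly intravenous dosing, the events were attributed to immune complexes in antibody-positive animals, none occurred at the highest dose, and the same section says that they are not considered predictive of human risk.
- A reader might expect local events to scatter over several PTs and SOCs. The documents give no coding convention that shows this, and Section 9.6.5 asks for the diagnosis in preference to single symptoms.

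**Conclusion.** The gap is real but confined to the summaries. As written, the Section 10.5 tables give the same 3/12 for per-injection rates of 4.2% and 25%, and they are not comparable between groups with different numbers of injections (34% against 47% at an assumed 10% risk). Over assumed risks of 5% to 30%, incidence after six injections runs from 26% to 88%. These percentages rest on assumed risks and independent injections. The identity of the 3/12 entries needs only that the reactions share a PT.

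A reader might infer that the information is lost or that the primary analysis is invalid. Neither follows: repeats stay visible in the listing, the worst grade is tabulated, and no test or threshold hangs on the incidence. It is a worthwhile, inexpensive improvement to how the primary endpoint is summarised.

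**What to change.** Keep the subject-incidence and severity tables. In Section 10.5 and the SAP, before the first DMC meeting:

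1. Define frequency as both the number of subjects and the number of events, and add the number of events to each TEAE table.
2. Add a descriptive summary of injection-site and study-knee reactions by injection number (1 to 6), with injections given as the denominator. Use a fixed window, such as 14 days after each injection, the sixth included. Because visit windows allow the next injection to fall inside 14 days, assign an event to the most recent injection.
3. Report exposure as number of injections and cumulative mg, since Section 4.1 allows the dose to change within a subject.
4. Show TEAEs separately up to 4 weeks after the last dose and after that point, and reconcile Sections 9.6.4 and 9.6.6 on active collection.
5. Reconcile the Week 12 endpoint wording in both the Synopsis and Section 4.1.

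Rates per unit of person-time are optional and supportive; they need not be primary.

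Cost: SAP wording and a few tables, some with small cells, mostly from injection records (Section 8.4) and AE onset dates (Section 9.6.5). One point needs checking on the AE form: the fields listed in Section 9.6.5 include neither the joint nor the onset time, although the Section 10.5 listing expects times. The form or the coding must identify study-knee events and place a same-day onset before or after the injection.
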